- **Blinding:** This will be a single blinded study and the NST-providers will be blinded to the treatment arm that the patient is assigned to. A clinician will initially interview the patient and at the time of enrollment into the clinical trial, obtain an informed consent after which the patient will be enrolled in the study.
- **Blinding the patients is not possible** due to several reasons:
 - o SQ53 and alcohol wipes will have labels on them
 - o differences in physical characteristics (smell) which are distinct for alcohol wipes and SQ53
 - o therefore, it is unfeasible to blind patients to the intervention.
- **However,** despite being an unblinded study, outcome of our study is not likely to be affected as the primary outcome measure is diagnosis of CRBSI which is based on the Positive Blood Culture and is not very likely to be impacted by a placebo effect.
- **Randomization with a placebo:** Once patients are enrolled into our study, patient's information will be discussed with the pharmacy who will assign the patient to either a treatment or a placebo group.

- Patients will be randomized in 1:1 ratio to receive either SQ53 or placebo. The randomization process will be stratified randomization, followed by blocked randomization in each stratum. Stratification will be done on two factors: CRBSI risk category and catheter type. CRBSI risk categories will be determined by the clinicians or NST staffs 1. High risk (1 or more CRBSI in previous 6 months) 2. Low risk (no CRBSI in previous 6 months) 3. New patient. Catheter types will be 1. Tunneled central catheters 2. Non-tunneled central catheters. The design has $3 \times 2 = 6$ strata. Blocked randomization will subsequently done in order to avoid serious imbalance in the number of participants assigned to treatment or placebo group. The block sizes will be determined by Cleveland Clinic Home Infusion Pharmacy.

Intervention:

Patients who qualify to enroll in the trial and sign an informed consent will be enrolled and will be eligible to receive either the intervention or the placebo. Providers will be blinded to which group patient is assigned to.

- Pharmacy (Cleveland Clinic Home Infusion Pharmacy will perform randomization and will assign patients to the groups)
- **All patients in the study will receive the wipes (Treatment group = SQ53 wipes, Placebo = alcohol wipes)**
 - o Provide packs of sterile wipes to the patient for daily use (**external use only**)

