3. Patients whose compliance is less than 90 percent will be excluded from Per Protocol analysis; however, those patients will be accounted in intention to treat analysis. Patients who developed skin reaction in remote site (e.g., forearm) will be excluded from Per Protocol analysis, but will be included in intention to treat analysis
 - a. Compliance will be determined by HPN dietitian at the time of phone/virtual visit encounters: patient will be asked about their disinfectant wipe use and compliance.
4. Our primary outcome measure (as listed in above data sheet) will be differences in the CRBSI rate at 6 months after patient enrollments into the trial (i.e. SQ53 use). We will also perform sub-analysis by utilizing patients as their own controls. Please see the detailed timeline below.
5. We will also analyze the differences in the number of admissions for CRBSI (which would include admission with suspect CRBSI), as well as, overall number of catheters changed for confirmed and suspected CRBSI.
6. We will perform Poisson Regression analysis to compare the rates and 95 % confidence interval of the differences in CRBSI rates and CRBSI admissions.
7. We will also perform a descriptive analysis identifying the most common microorganisms causing the CRBSI in the periods both before and during the SQ53 therapy.
8. We will also perform a survival analysis to plot a Kaplan-Meier curve

9. We will collect mortality data of patients. We will report an overall mortality, as well as, CRBSI-specific mortality in patients using SQ53 for CRBSI prevention.

Sample size and power calculation:

1. In the un-published study conducted in India SQ53 has been reported to reduce the CRBSI rate by 94%. We expect this effect size to be lower in our cohort. We performed our sample size calculation by utilizing the data reported in our previous study which reported CRBSI rates in high risk PN patients (Pre-ELT CRBSI rate= 3.53 and post-ELT 1.65 per 1,000 catheter days). Considering current CRBSI rate in our high-risk population to be 1.65 per 1000 catheter days, we will need a sample size of 46 patients to identify a 50% reduction in CRBSI rate with alpha of 0.05 and 80 % power.

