2. To account for the patient attrition due to mortality, lost follow up and non-compliance (for per-protocol analysis), we would like to increase our sample size by 30% to this estimated calculation and would need to enroll 30 patients in each group of our study to make determinations of differences with statistical significance.

Safety concerns: Risk to the study participants: Minimal

1. Our study is a single blinded randomized placebo-controlled phase III clinical trial which utilizes disinfectant wipes which are meant for external use only. These wipes have proven to be safe in the in-vivo and in-vitro studies.
2. No major adverse effect has been reported in previous clinical trial.
3. Current data suggest that SQ53 has no potential for skin irritation; however, if a patient experiences hypersensitivity skin reaction to any of the ingredients in the formula, then those patients will be excluded from the study and use of wipes will be discontinued.
4. Collected PHI data will be securely protected on the Cleveland Clinic Network drive.

Timeline:

Please see below a simplified timeline for this project.

Time Period	Activity
-------------	----------

	
Project Lead: [name]
 
Project mentors: [name] and [name]
 
Project team members: [name], [name], [name] and [name], [name], [name]

June 2020 - Sept 2020	
 1. Protocol and team development 2. Investigational New Drug (IND exemption process) 3. FDA exemption given by CCF IDE office considering the wipes as low risk device 
Personnel responsibility:
 
Above steps have been completed

Oct 2020 – Nov 2020	
 1. Protocol submission to CHN & budget acquisition 2. Protocol submission to DDSI 3. Protocol submission to IRB 
Personnel responsibility:
 
Above steps have been completed.
 
 - Protocol for IRB/CHN/DSFI submission is ready - Cover letter is ready - Informed consent document is ready - Budget is done

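### The only time-to-event method is a Kaplan-Meier curve with no stated event or censoring rule; if it censors death and permanent end of PN, it overstates the 6-month proportion with CRBSI by a small amount in both arms

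*Combined protocol and SAP*

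**What the plan says.** The section on data protection, processing and analysis gives the time-to-event plan in item 8: "We will also perform a survival analysis to plot a Kaplan-Meier curve". It states no event, time origin, censoring rule or between-arm test, and no other time-to-event method appears in the document.

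The surrounding items give the context:

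- Item 4 sets the primary outcome as "differences in the CRBSI rate at 6 months after patient enrollments into the trial".
- Item 6 gives the comparative method: "We will perform Poisson Regression analysis to compare the rates and 95 % confidence interval of the differences in CRBSI rates". The offset is not stated.
- Item 9 says that mortality will be collected and reported, without linking it to the curve.

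Three other places bear on whether patients can leave the risk of CRBSI within 6 months:

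- Sample size and power calculation, item 2, raises enrolment by 30%. Its reason begins "To account for the patient attrition due to mortality, lost follow up and non-compliance (for per-protocol analysis".
- The Introduction says that PN may last from weeks to years, and that many patients need it for life.
- The recruitment section makes patients who are new to PN, or on it for less than 6 months, one of the three risk categories.

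**The concern.** A patient who has died, or who has stopped PN for good and no longer has a catheter, cannot develop a CRBSI. A Kaplan-Meier curve for first CRBSI, drawn in the usual way, censors that patient. It then estimates the risk that would apply if the patient were still exposed. Readers commonly take one minus the curve at 6 months as the share of patients infected, and on that reading it is too high whenever such events occur.

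The absolute gap between arms is affected too. The Kaplan-Meier gap need not equal the actual difference in the proportion infected, above all if deaths or ends of PN are unequal between arms. At stake is how a supplementary figure is read, not the primary test.

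**Working it through.** The documents state no 6-month CRBSI risk, so there is no planned figure to reproduce. The check compares the two estimators on the plan's own rate.

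**Inputs**

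- Control rate: 1.65 per 1000 catheter-days, from the sample-size section ("Considering current CRBSI rate in our high-risk population to be 1.65 per 1000 catheter days"). It is used here as a constant hazard of first CRBSI.
- SQ53 rate: 0.825 per 1000 catheter-days, from the planned 50% reduction.
- Follow-up: 6 months, taken as 182.5 days.
- Arm size: 30 per group, with 1:1 allocation.
- Competing-event probability q over 6 months, in the absence of CRBSI: **assumed**, 2% to 30%. The top of the range borrows the 30% attrition allowance as an upper bound. That allowance also covers loss to follow-up and non-compliance, which are not competing events.

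**Formulas** (constant, independent cause-specific hazards)

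- H = rate × 182.5, so control H = 0.00165 × 182.5 = 0.3011 and SQ53 H = 0.000825 × 182.5 = 0.1506.
- One minus Kaplan-Meier, competing events censored: 1 − exp(−H).
- Actual cumulative incidence: H/(H+G) × [1 − exp(−(H+G))], with G = −ln(1 − q).

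**Kaplan-Meier.** Control: 1 − exp(−0.3011) = 26.0%. SQ53: 1 − exp(−0.1506) = 14.0%. Difference 12.0 points, ratio 0.538.

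**Worked case, control, q = 10%.** G = 0.1054 and H+G = 0.4065. The cumulative incidence is 0.3011/0.4065 × (1 − exp(−0.4065)) = 0.7408 × 0.3340 = 24.7%.

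**Same q in both arms**

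| q | Control | SQ53 | Excess of 1−KM, control / SQ53 (points) | Risk difference (points) | Risk ratio |
|---|---|---|---|---|---|
| 2% | 25.8% | 13.8% | 0.2 / 0.1 | 11.9 | 0.537 |
| 10% | 24.7% | 13.3% | 1.3 / 0.7 | 11.5 | 0.537 |
| 30% | 22.1% | 11.8% | 3.9 / 2.2 | 10.3 | 0.535 |

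In relative terms the excess is about 1% at q = 2%, 5% at 10% and 18% at 30%. The risk ratio barely moves.

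**Unequal q.** With 10% in control and 30% on SQ53, the actual difference is 24.7 − 11.8 = 12.9 points. With 30% in control and 10% on SQ53, it is 22.1 − 13.3 = 8.8 points. Kaplan-Meier shows 12.0 points in both cases.

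**No effect on the CRBSI hazard.** With 1.65 per 1000 catheter-days in both arms and q of 10% against 30%, both Kaplan-Meier curves reach 26.0%. The cumulative incidences are 24.7% and 22.1%.

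**Scale.** With 30 per arm, the standard error of the 6-month risk is √(0.26 × 0.74/30) = 8.0 points in control and √(0.14 × 0.86/30) = 6.3 points on SQ53. Expected first events, before allowing for competing events, are 30 × 0.260 + 30 × 0.140 = 12.

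**The case against.** The strongest reply is that item 8 adopts no wrong rule. It names no event, and a curve for death would not have this problem. Nor does Kaplan-Meier force these patients to be censored: with a fixed 6-month horizon they could be kept in the risk set to day 182.5, and with no other censoring one minus Kaplan-Meier would then equal the cumulative incidence. This stands in part: the defect is an omission. But items 4 to 7 concern CRBSI and mortality has its own item 9, so first CRBSI is the natural event, and censoring at death or end of PN is the usual practice if nothing else is written.

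A second reply is that no conclusion rests on the curve. That stands: rates are compared by Poisson regression, which does not have this bias if catheter-days at risk are the offset.

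A third is that the size is not in the documents. That also stands. No frequency of death or end of PN is given, and because many patients need PN for life, competing events are to be expected but their number is unknown.

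A reader might also infer that unequal deaths or ends of PN would drive the Kaplan-Meier curves apart for reasons other than CRBSI. The plan gives no ground for this. Under independent hazards those curves depend only on the CRBSI hazard, and it is the cumulative incidence curves that would separate. Separation of the Kaplan-Meier curves would need informative censoring, for which the documents offer no evidence.

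**Conclusion.** The point holds as a minor improvement. If the item 8 curve is for first CRBSI and censors death and permanent end of PN, it overstates the 6-month proportion infected in both arms. In the control arm the excess is about 0.2 points at an assumed 2% competing-event probability, 1.3 at 10% and 3.9 at 30%, all below the standard error of about 8 points. With equal competing events the ratio is almost unchanged; with unequal ones the Kaplan-Meier gap can differ from the actual gap by up to about 3 points in the cases tried (12.0 against 8.8).

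These figures rest on constant and independent hazards, on a control rate that the plan quotes for its high-risk patients, and on assumed competing-event probabilities. It would go too far to conclude that the primary result is biased. Item 6 compares rates, and the only open matter there is the unstated offset.

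**What to change.** Amend item 8 as follows:

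- Name first CRBSI, timed from randomization, as the event.
- Plot the Aalen-Johansen cumulative incidence by arm in place of the Kaplan-Meier curve.
- Treat death, and permanent end of PN with catheter removal, as competing events. Catheter replacement with continued PN does not end the risk and is not one.
- Censor that curve at loss to follow-up or at 6 months.
- If a between-arm time-to-event comparison is wanted, use a cause-specific hazard ratio, which does censor at competing events. Label it supportive, since only about 12 first events are expected.

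It would also help to state in item 6 that catheter-days at risk are the Poisson offset.

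The cost is a few lines of text and standard software, with no added patients or visits. The one practical step is for the sponsor to confirm that the dates of death, end of PN and permanent catheter removal are held in the home PN database. The documents mention only mortality data and counts of catheters changed for confirmed or suspected CRBSI.

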STUDY PROPOSAL

Title: SQ53 disinfectant wipes for prevention of catheter related blood stream infection in patients receiving home parenteral nutrition:

A Single Blind Randomized Placebo-controlled Clinical Trial

(NCT04822467)

Principal Investigator: [name]

Co-investigators: [name], [name] [name], [name], RD, [name], [name], RD, [name], [name], [name], [name], [name], [name], [name], RD, [name], NP, [name], PA.

Introduction:

Parenteral nutrition (PN) therapy is an essential component of medical management of patients suffering from intestinal failure. Depending on the underlying etiology and the type of intestinal failure, the duration of parenteral nutrition therapy could range from several weeks to several years, although a substantial proportion of these patients also require lifelong parenteral nutrition support. These patients continue the infusion of PN at their homes and are managed by the Cleveland Clinic's Home PN support team. These patients require Central Venous Catheters (CVC) for prolonged period of time for infusion of parenteral nutrition. The two most commonly used central catheters for TPN infusion are the Peripherally Inserted Central Catheter (PICC) and Tunneled CVCs. Catheter related blood stream infection (CRBSI) is a major complication of long-term CVCs. CRBSI is associated with high morbidity, mortality and healthcare

Protocol version: 1.27.2022

cost. Additionally, CRBSI can also lead to an interruption in nutrient delivery, loss of work and productivity, premature vascular access device removal, and poor quality of life.

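### No report of deaths by randomised arm is planned: the mortality sentence names only SQ53 users, although the trial is randomised 1:1 with an intention-to-treat analysis

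*Combined protocol and SAP*

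**What the plan says.** The combined protocol and SAP deals with mortality in item 9 of the section on data protection, processing and analysis. The item has two sentences. The first is about collection and names no arm: "We will collect mortality data of patients". The second is about reporting: "We will report an overall mortality, as well as, CRBSI-specific mortality in patients using SQ53 for CRBSI prevention".

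The design supplies a concurrent comparator. Under Blinding and Randomization: "Patients will be randomized in 1:1 ratio to receive either SQ53 or placebo". The sample size section says the investigators "would need to enroll 30 patients in each group of our study". Items 2 and 3 of the analysis section plan an intention-to-treat analysis beside a per-protocol one.

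The document treats death as a relevant event. The Introduction states that "CRBSI is associated with high morbidity, mortality and healthcare" cost are linked, and item 2 of the sample size section inflates enrolment "To account for the patient attrition due to mortality, lost follow up and non-compliance".

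**The concern.** In a randomised trial, the control arm shows what would have happened without the intervention. A death count confined to SQ53 users sets that aside. In patients with intestinal failure some deaths may occur whatever wipe is used, so a reader given the SQ53 count alone cannot say whether it is high, low or expected.

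There are two further consequences. Death ends a patient's time at risk of CRBSI, so deaths by arm help a reader interpret the 6-month CRBSI rates. And a group defined by using SQ53 differs from the group randomised to SQ53: a patient who stopped the wipes may fall out of the count.

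**Working it through.** **1. Is a by-arm report of deaths planned anywhere else?** Each place that could supply one, in turn:

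- Analysis item 5 plans differences for CRBSI admissions and catheter changes. Deaths are not included.
- Analysis item 6 applies Poisson regression to CRBSI rates and CRBSI admissions. Deaths are not included.
- Analysis item 8 plans a Kaplan-Meier curve without naming an endpoint, groups or a test.
- The sample data sheet under Data collection has columns for confirmed CRBSI, CRBSI admissions and catheter changes. It has no column for death.
- The study objectives list CRBSI prevention (primary) and adverse effects (secondary). Mortality is not named.

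None supplies it.

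**2. Planned denominator.** The plan's own figure is 46 patients plus 30%: 46 × 1.30 = 59.8, rounded to 60, or 30 per arm. This reproduces. Whether 46 is itself adequate is a separate question and does not bear on this point.

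**3. What an SQ53-only count would show.** Clopper-Pearson 95% limits for x deaths in n = 30: the lower limit is the 0.025 quantile of Beta(x, n − x + 1) and the upper limit is the 0.975 quantile of Beta(x + 1, n − x). For x = 0 the upper limit is 1 − 0.025^(1/30) = 11.6%.

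| Deaths of 30 | Observed | Exact 95% limits |
|---|---|---|
| 0 | 0% | 0% to 11.6% |
| 1 | 3.3% | 0.1% to 17.2% |
| 2 | 6.7% | 0.8% to 22.1% |
| 3 | 10.0% | 2.1% to 26.5% |

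The documents state no expected mortality, so there is nothing to set these against. The width itself reflects small numbers and remains after any change of wording. What the change adds is the comparison.

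**4. Effect of a use-defined group.** Let D of N patients randomised to SQ53 die, and let s of them stop the wipes, of whom d die. The rate among users is (D − d)/(N − s). It exceeds D/N when d/s is below D/N, and is less than D/N when d/s is above it. With N = 30, D = 2 and s = 1, the randomised-arm figure is 2/30 = 6.7%. The user figure is 2/29 = 6.9% if the stopper survived and 1/29 = 3.4% if the stopper died. The direction is unknown.

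**5. What 30 versus 30 can deliver.** Control mortality of 2% to 20% is an assumption.

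- Expected control deaths: 30 × 0.02 = 0.6 to 30 × 0.20 = 6.
- Power to detect a halving (two-sided 0.05): 5% to 19% by normal approximation, 0% to 10% by Fisher's exact test.
- Power to detect a doubling (Fisher): 0.06% to 30%.
- Patients per arm for 80% power to detect a halving: 2319 at 2%, 435 at 10%, 199 at 20%.
- With 0 deaths in one arm, 5 in the other gives Fisher p = 0.052 and 6 gives p = 0.024.
- With 2 deaths in each arm, the Wald half-width for the difference is 1.96 × √(2 × 0.0667 × 0.9333/30) = 0.126, about 13 percentage points.

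Reporting by arm is therefore descriptive.

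**The case against.** Four points can fairly be made for the plan.

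- **The restriction to SQ53 may not be meant for both measures.** A reader might infer that all mortality will be reported for SQ53 patients only. The text does not say so outright. Collection is unrestricted, and the closing phrase of item 9 could qualify CRBSI-specific mortality alone. The document also uses SQ53 loosely for trial participation: analysis item 4 glosses enrolment as SQ53 use, and the data sheet labels placebo patients' rows by SQ53 trial enrolment. This stands, so exclusion of the control arm is an inference, though the most natural one. It does not rescue the plan. On the alternative readings, overall mortality is pooled or its groups are left unstated, and no reading yields deaths by arm.
- **Intention to treat covers the patients who stop.** Analysis item 3 keeps remote-site skin reactors and patients with low compliance in the intention-to-treat set. That stands in part. Item 9 does not refer to that set, and item 3 under Safety concerns says patients with a hypersensitivity reaction are excluded from the study. The two passages need to be reconciled.
- **No direction of bias is shown.** A reader might infer that dropping stoppers makes SQ53 look safer. The documents do not support this: such patients leave both numerator and denominator, and nothing shows that they die more often.
- **Sixty patients cannot settle mortality, and it is not a listed objective.** Both are true. They limit what the comparison can show and the weight of the point. They do not justify reporting without the other arm.

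**Conclusion.** The point holds as a gap in safety reporting of moderate weight. Item 9 names a use-defined and apparently single-arm group, and no part of the document plans a between-arm report of deaths, although randomisation provides the comparator. An SQ53-only count could not be interpreted: 0 of 30 allows a true risk of up to 11.6%, and 2 of 30 allows 0.8% to 22.1%, with no reference value given. Omitting patients randomised to SQ53 who stopped could bias it in an unknown direction.

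A reader might also infer that adding the control arm would reveal benefit or harm on mortality. It would not. Across assumed control mortality of 2% to 20%, power to detect a halving is at most about 19%. The gain is a concurrent reference and an honest interval. The primary CRBSI analysis is unaffected.

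The conclusion rests on the planned 30 per arm and on the absence of any other mortality analysis in the document. The mortality range bears only on the power figures.

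**What to change.** Replace the reporting sentence of item 9 with: *Overall and CRBSI-specific deaths will be reported descriptively by randomised arm for all randomised patients over the same 6-month window, regardless of whether wipes were stopped, with the between-arm difference and 95% CI.*

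This applies the intention-to-treat principle already planned and makes clear which groups the sentence covers. The cost is one table column and a wide interval, which should be presented as descriptive. Collection is already not restricted by arm, though follow-up of vital status should continue to 6 months in patients who stop the wipes.

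One optional addition: the document neither defines a CRBSI-specific death nor says who decides. A short definition would help, but it is extra work. The blinded NST providers may also learn the allocation, because patients know their wipe and only the SQ53 group has the skin test.

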 - o Wipes should be used daily, as well as, when the dressing is changed, by wiping the catheter surface and hubs for at least 15 seconds
 - o **Daily use:** Patients will be given instruction to clean the exterior and the caps of the intravenous catheters by following a sterile technique. This should be done before and after each use (i.e. PN infusion)
 - o **At the time of dressing change:** Standard practice is to change the dressing every week. At this time the patient will use wipes to clean the catheter exit site and skin around the catheter exit site, catheter exterior and catheter caps prior to applying the new dressing
 - o Wipes will be provided to the patient free of cost (material will be sponsored by the JVS company)

- Patients in both the groups will continue to use the standard care: i.e. ethanol (curos) caps, saline locks.

Data collection:

1. A registry of enrolled patients will be prepared. CCF HPN service has an approved database of patients receiving home parenteral nutrition. There are no additional HPI that will be collected as a part of enrollment in the study. The patient data is already collected into a password protected HPN database as current standard of practice. This data is routinely collected and updated by HPN dietitians.

Sample data sheet of primary objectives (data in *italics blue font* is for example):

Patient Nomenclature:				
SQ53/Treatment Group: Patient T1, Patient T2....				
Placebo Group: Patient C1, Patient C2....				
	Pre vs Post SQ53 trial enrollment	Number of Confirmed CRBSI in 6 months	Number of total admissions for CRBSI in 6 months	Number of catheters changed due to CRBSI in 6 months
Patient T1	Pre	2	3	0
	Post	0	1	0
Patient T2	Pre			
	Post			
Patient C1	Pre	0	1	0
	Post	1	1	1

Patient C2	Pre			
	Post			
Patient C3	Pre			
	Post			

Data protection, processing and, analysis of the data:

1. CCF HPN service has an approved database of patients receiving home parenteral nutrition. The patient data is already collected into a password protected HPN database as current standard of practice. We will use REDCap for data entry for analysis. All data will be password protected.
2. We plan to perform both "**Per Protocol**" and "**Intention to treat analysis**".

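### 46 patients (60 enrolled) followed for 6 months give about 20% power for a 50% reduction in CRBSI, not the stated 80%

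*Combined protocol and SAP*

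**What the plan says.** Item 1 of *Sample size and power calculation* fixes the control rate, "Considering current CRBSI rate in our high-risk population to be 1.65 per 1000 catheter days", and derives a "sample size of 46 patients to identify a 50% reduction in CRBSI rate with alpha of 0.05 and 80 % power". Item 2 adds 30% for attrition and non-compliance and concludes that the investigators "would need to enroll 30 patients in each group of our study to make determinations of differences with statistical significance". Since 46 × 1.3 = 59.8, the 46 is a total, not a number per group.

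Item 4 of *Data protection, processing and, analysis of the data* defines the primary outcome as "differences in the CRBSI rate at 6 months after patient enrollments into the trial". The sample data sheet under *Data collection* also counts confirmed infections over 6 months. Item 6 of the analysis section compares rates by Poisson regression with a 95% confidence interval. The sample size section gives no catheter-days per patient, sidedness, formula or expected number of infections.

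On background care, *Intervention* states: "Patients in both the groups will continue to use the standard care: i.e. ethanol (curos) caps, saline locks". Low-risk and new patients are eligible alongside high-risk ones.

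**The concern.** The power of a comparison of rates depends on the number of events, and so on rate × patients × time. The plan states a rate and a number of patients but no time. With the 6 months that the outcome definition implies, 46 patients should produce about 10 infections in all, far too few to detect a halving with 80% power.

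The trial is presented as phase III, and the plan says that its size allows differences to be determined with statistical significance. If power is really near 20%, the trial will most likely miss a true halving of the infection rate, and a non-significant result could be read as showing that the wipes do not work. Ethics reviewers, participants and later readers would be relying on a wrong figure.

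**Working it through.** **Inputs**

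- Control rate 1.65 and treated rate 0.825 per 1,000 catheter-days; alpha 0.05; power 80% (*Sample size*, item 1).
- 1:1 allocation (*Blinding and Randomization*).
- Follow-up 6 months, taken as 182.5 catheter-days (*Data protection…*, item 4). This assumes a catheter in place every day and no dropout, so it is an upper limit.
- Sidedness is not stated, so both are shown. (z_α + z_β)² = 6.183 one-sided and 7.849 two-sided.

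**Formulas**, with λ₁ and λ₂ the expected infections per patient:

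- Rate difference: n per arm = (z_α + z_β)² (λ₁ + λ₂) / (λ₁ − λ₂)²
- Log rate ratio: n per arm = (z_α + z_β)² (1/λ₁ + 1/λ₂) / [ln(λ₁/λ₂)]²

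**Step 1: recover the 46.** Take the rates per 1,000 days as if they were means per patient (λ₁ = 1.65, λ₂ = 0.825).

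- One-sided: 6.183 × 2.475 / 0.6806 = 22.5, so 23 per arm and **46 in total**.
- Two-sided: 7.849 × 2.475 / 0.6806 = 28.5, so 58 in total.

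This amounts to 1,000 catheter-days (2.7 years) per patient. The *Timeline* runs from December 2020 to December 2021, about 13 months. No two-arm method tried at 182.5 days gave 46: rate methods gave 238–258 one-sided and 300–326 two-sided, and comparing 6-month risks (26.0% versus 14.0%) gave 272–378.

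**Step 2: sample size at 6 months.** λ₁ = 1.65 × 0.1825 = 0.301 and λ₂ = 0.151. Two-sided:

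- Difference: 7.849 × 0.4517 / 0.02267 = 156.4 per arm, or 314 in total.
- Log: 7.849 × 9.963 / 0.4805 = 162.8 per arm, or 326 in total.

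One-sided totals are 248 and 258.

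**Step 3: expected infections.** 46 patients: 23 × 0.301 = 6.9 versus 3.5, about 10 in all. 60 patients: 9.0 versus 4.5, about 14 in all. The two-sided requirement for a ratio of 0.5 is 66 events (Schoenfeld: 4 × 7.849 / 0.4805) to 71 (Freedman: 7.849 × 9).

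**Step 4: power.** On the difference scale, power = Φ[(λ₁ − λ₂)/√((λ₁ + λ₂)/n) − z_α]. For 30 per arm, two-sided: 0.1506 / √(0.4517/30) = 1.227, and Φ(1.227 − 1.960) = 0.23. The table gives the difference and log scales together, for a 50% reduction.

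| Control rate | Days per patient | Sides | 46 patients | 60 patients |
|---|---|---|---|---|
| 1.65 | 182.5 | 2 | 18–19% | 22–23% |
| 1.65 | 182.5 | 1 | 28% | 33–34% |
| 1.65 | 365 | 2 | 32–33% | 40–41% |
| 1.65 | 365 | 1 | 44–45% | 52–54% |
| 3.53 | 182.5 | 2 | 34–35% | 42–43% |
| 3.53 | 182.5 | 1 | 46–47% | 55–56% |
| 3.53 | 365 | 2 | 59–60% | 70–72% |
| 3.53 | 365 | 1 | 70–72% | 80–81% |

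With so few events the approximation is rough, so the first row was checked by enumerating both Poisson counts. Across exact conditional, score, likelihood-ratio and log-Wald tests, power is 10–23% with 46 patients and 16–26% with 60.

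**Step 5: what 60 patients can show** (6 months, two-sided).

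- At 1.65, 80% power exists only for a reduction of about 87% (likelihood ratio) to 96% (exact conditional). At 3.53, for about 70–74%.
- For a true ratio of 0.5 at 1.65, the standard error of the log ratio is √(1/9.03 + 1/4.52) = 0.576. The expected 95% interval is 0.5 × exp(±1.96 × 0.576), about 0.16 to 1.55.
- At 3.53, a 50% reduction needs 148–154 patients.

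**The case against.** - **Sidedness.** The plan does not state it, and 46 is matched exactly only by a one-sided calculation. On that basis the fair figures are 28% (46 patients) and 33–34% (60), not about 20%. This stands as a reason to report both. The planned 95% confidence interval points to a two-sided test, and neither version approaches 80%.
- **The 1,000-day explanation is inferred.** This also stands: no text says that this exposure was used. The finding does not depend on it, because 46 does not follow from the stated rate and 6 months however it arose.
- **Longer exposure or a higher rate.** The *Timeline* continues the study for another 6 months, so early patients might contribute more time. A full year at 1.65 gives at most about 55% power, even one-sided and by the most favourable test. About 80% is reached only by combining the 3.53 rate, 365 days for every patient, all 60 retained and a one-sided test. That departs from both the stated rate and the stated outcome.
- **The rate mismatch has no clear net direction.** Saline rather than ethanol locks would probably raise the control rate, and low-risk and new patients would probably lower it. The 3.53 figure also comes from high-risk patients. So the mismatch is a reason to justify the input, not evidence that power is higher or lower than shown.

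**Conclusion.** The concern holds. With the plan's own rate, effect and 6-month outcome, power is about 18–19% with 46 patients and 22–23% with 60 at two-sided 0.05, against the stated 80%. The number needed is about 314–326, roughly seven times 46 (314/46 = 6.8).

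These figures assume Poisson counts, full catheter exposure for 182.5 days and no attrition. The plan itself expects attrition, and variation in risk between patients beyond Poisson would lower power further, so they lean towards the favourable side. The conclusion is unchanged by the choice of test, by sidedness, or by using 3.53 as the control rate over the planned 6 months. This is an error in a figure that the trial relies on and must be corrected.

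**What to change.** Replace the power claim in items 1 and 2 of *Sample size and power calculation* with a statement on these lines:

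> With 60 patients each followed for 6 months (at most 182.5 catheter-days), no more than about 14 CRBSIs are expected at a control rate of 1.65 per 1,000 catheter-days and a 50% reduction. Power for that reduction (two-sided alpha 0.05) is about 22% at a control rate of 1.65 and 42% at 3.53. Power of 80% is available only for reductions of about 87–96% and 70–74% respectively.

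Also:

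- state the follow-up time, the sidedness and the formula;
- justify a control rate for saline locks and the enrolled mix of risk groups, or show a range;
- delete the promise of statistical significance;
- say that a non-significant result will not show lack of effect and that the rate ratio with its 95% interval is the main result.

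Restating costs only protocol wording and needs no extra patients, though the stated power becomes much less favourable. Calling the trial a pilot or estimation study would describe it honestly but is optional. If the sponsor wants to keep the 80% claim, the alternative is more patients, longer follow-up or both: about 314–326 evaluable patients at 6 months and 1.65, before any allowance for attrition.
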